6. TREATMENT OF SUBJECTS

Approximately 40 subjects with either OAG or OHT will be enrolled, with a target completion of 36 subjects. Patients will be randomized in a 1:1 ratio to receive 1 % Nyxol or placebo once daily for 14 days beginning at 8PM to 10PM on Day 1 (Baseline Visit) and continuing through Day 14. IOP evaluations will take place at 8AM, 10AM, and 4PM on Day 8 \pm 1 Day and on Day 15 \pm 1 Day, and at 8AM on Day 16. All IOP measurements have a window of \pm 15 minutes with at least 2 hours between the 8AM and 10AM assessments. There will be a Follow-up phone telephone call 7 days after the last Treatment-study Visit (Day 22).

6.1. Treatment adherence

All subjects will be instructed on the importance of following the once-a-day dosing regimen. Beginning the day of the Baseline Visit (Day 1) subjects will instill one drop of study medication in each eye at 8PM to 10PM and repeat this procedure 13 times for a total of 14 doses. Subjects are to bring unused bottles into the study site on the Day 8 Visit and the Day 15 Visit. Treatment adherence will be measured by counting the dropper bottles at the start of the study, and those remaining at each study visit.

6.2. Concomitant medications

As noted in the exclusion criteria ([Section 5.2](#)), the following are prohibited:

- Use of ocular medication within 30 days of the Screening Visit, or anticipated use during the study, with the exception of lubricating drops for dry eye (preservative-free artificial tears), which may be used throughout the study.
- Use of any topical or systemic adrenergic or cholinergic drugs up to 30 days prior to Screening, or during the study unless the drug, dose and regimen has been consistent for the 30 days prior to Screening ([Appendix 1](#)). A large number of drugs, both prescription and over-the-counter, contain active ingredients that can affect intraocular pressure. This would include many eye drops, such as Visine, that would be used to reduce redness, most cough or cold preparations, antihistamines and bronchodilators, most nose-drops, most blood-pressure medications, many drugs used for migraines, and many other products. ***If there is any question about whether a medication is acceptable, Ocuphire or the Medical Monitor should be consulted before proceeding.***
- Changes in systemic medication that could have an effect on ocular autonomic tone 30 days prior to Screening or anticipated during the study.

Intermittent use of over-the-counter (OTC) ***preservative-free*** artificial tear lubricant products is acceptable. However, no other ocular medications (OTC or prescription) are allowed within 30 days of the Screening Visit, or during the study.

Topical or systemic therapy with agents that could have an effect on IOP is to be consistent in dose, regimen and agent within the 30 days prior to Screening and throughout the study. For example, a subject can be treated with a systemic adrenoceptor antagonist as long as the particular agent and its dose and regimen had been consistent for the thirty 30 days prior to Screening, and there was no reason to believe that alteration would be necessary at some point later during the study.

Use of all medications should be documented on the appropriate CRF. Investigators are encouraged to contact Ocuphire or the Medical Monitor for any questions regarding

allowed medications. Judgment of continued study participation by the subject, and inclusion of this subject's subsequent visits in the safety and efficacy analysis will be made by Ocuphire.

All medications which the subject has taken within 30 days prior to the Screening Visit and during the study will be recorded in the CRF. The name of the drug, dose, route of administration, duration of treatment and indication will be recorded for each medication. For combination products (e.g., Contac®), the brand name is required. For non-combination products, the generic name is desired. The use of routine ophthalmic diagnostic pharmaceutical agents (e.g., fluorescein and local anesthetic) will be allowed, and individual documentation not required. Any change in dosing parameters should also be recorded in the CRF.

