2. INTRODUCTION

2.1. *Investigational products*

The test product is Nyxol Eye Drops - 1% phentolamine mesylate ophthalmic solution (Nyxol), an alpha-1-adrenergic antagonist. Placebo control is Nyxol vehicle alone.

2.2. *Findings from nonclinical and clinical studies*

Detailed findings from nonclinical and clinical studies and potential risk are provided in the Investigators' Brochure (IB) (January 2019).

Single Dose Phase 2:

In NYX-SNV, treatment of 16 subjects with severe night vision disturbances with a single dose of 1% Nyxol resulted in [REDACTED]

Statistically significant improvements in several measurements of visual function as well as wavefront aberrometry were also reported. Modest, transient increases were seen in conjunctival and bulbar hyperemia.

Multiple Dose Phase 2:

In NYX-01a2, (Ocularis IND 70-499) 60 otherwise healthy subjects with reduced mesopic contrast sensitivity (CS), divided into three groups of twenty subjects each, received placebo, 0.5% or 1.0% Nyxol for 15 days, followed by an optional two week period where the subjects could use up to six doses of 1.0% Nyxol as needed.

IOP was measured 2 hours after the first dose on Day 1, and then again on Day 32 that was at least three days after the last dose. The mean absolute IOP and mean IOP changes post treatment on Day 1 were statistically significant between the treatment arms and the placebo arm.

[REDACTED]

More than 100 subjects have received active doses of Nyxol ranging from 0.2% to 1.0% in Phase 1 and Phase 2 clinical trials. There have been no serious adverse events. All treated subjects developed some degree of conjunctival hyperemia, an average of one point increase on a four point CCLRU scale (none, mild, moderate, severe). Most subjects went from mild to moderate. Three went from mild to severe. All redness resolved within 8 hours.

The anticipated benefits of the proposed study are reduction in IOP and improvement in the signs and symptoms of open angle glaucoma and ocular hypertension. The risks determined in previous ophthalmic studies are local hyperemia and conjunctival injection.

Systemic risks, principally tachycardia and hypotension, are known from parenteral administration of doses of 5 mg phentolamine mesylate (Regitine, Bedford, Ohio; see Regitine

Prescribing Information in IB) and local injectable administration of OraVerse (Novalar, San Diego, California; see OraVerse Prescribing Information in IB).

Design justification

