In previous clinical studies of Nyxol the most frequently reported adverse event was conjunctival hyperemia. **In the present study, investigators are cautioned to use the appropriate verbatim term on the adverse event form to describe this observation:**

- **Redness related to instillation that is transient (i.e., is no longer present 2 hours after instillation) = “conjunctival erythema upon instillation”.**
- **Redness that is NOT transient (i.e., is present 2 hours after instillation) = “conjunctival hyperemia”.**

Investigators are also cautioned to appropriately note all observations of conjunctival hyperemia (also called conjunctival erythema) on the biomicroscopy CRF.

Expedited reporting of Serious and Unexpected Adverse Events: All treatment emergent SAEs (related and unrelated) will be recorded from the first administration of study medication, Baseline Visit (Day 1), until the final study visit, following the end of treatment exposure. Any SAEs “suspected” to be related to the investigational product and discovered by the Investigator at any time after the study should be reported.

Any SAE that occurs must be reported to Oculos within 24 hours of its occurrence or within 24 hours of learning of its occurrence. Recurrent episodes, complications, or progression of the initial SAE must be reported to Oculos as follow-up to the original episode within 24 hours of the Investigator receiving the information. Information about all SAEs will be collected and recorded on the SAE form. All pertinent medical records and information collected during the treatment and follow-up of the subject should be maintained at the site with a copy emailed to [contact]. The Investigator must assess the SAE relationship and complete the SAE form. Oculos may request additional information. Follow-up information (e.g., discharge summary) will be retained in the subject’s chart and a copy will be emailed to [contact]. In addition, all SAEs should be recorded on the Adverse Event CRF page with the serious question marked “Yes”.

It is the investigator’s responsibility to notify the approving IRB of any SAEs on a timely basis as instructed by the Sponsor following the Sponsor’s determination of causality. All subjects who experience an SAE should be followed clinically and undergo the appropriate diagnostic evaluations until stabilization or resolution of the event. The Sponsor/Oculos will report all SAEs to the US Food and Drug Administration (FDA) on the appropriate

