#### **7.1.4. Safety Population (SP)**

The Safety Population will include all randomized subjects who have received at least one dose of study medication. The Safety Population will be used to summarize safety variables. Subjects who are members of the Safety Population will be analyzed as treated.

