### **8.2. Protocol Deviations**

Major protocol deviations, as determined by a Sponsor blinded review of the data prior to database lock and unblinding of the study, may result in the removal of a subject's data from the PP Population. The Sponsor or designee will be responsible for producing the final deviation file; this file will include a description of the protocol deviation and clearly identify whether this violation warrants exclusion from the PP Population. This file will be finalized prior to database lock.

All protocol deviations will be presented in a by-subject data listing, with a flag to indicate if a deviation was considered major..

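### Protocol 6.2 lets the sponsor decide, without criteria or timing, whether a subject's visits after a medication question enter the safety analysis, which conflicts with the Safety Population and SAP 8.2

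*Protocol*

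**What the plan says.** Protocol 6.2 restricts concomitant medication. Apart from preservative-free artificial tears, "no other ocular medications (OTC or prescription) are allowed within 30 days of the Screening Visit, or during the study". On drugs that can affect IOP it says: "This would include many eye drops, such as Visine, that would be used to reduce redness, most cough or cold preparations, antihistamines and bronchodilators", and the list goes on to nose-drops, blood-pressure drugs, migraine drugs and others. After inviting questions about which medications are allowed, it leaves to the sponsor the judgement of whether the subject continues, and says that "inclusion of this subject's subsequent visits in the safety and efficacy analysis will be made by Ocuphire".

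On the effect at issue, Protocol 8.3.1 says: "In previous clinical studies of Nyxol the most frequently reported adverse event was conjunctival hyperemia". Protocol 2.2 adds: "All treated subjects developed some degree of conjunctival hyperemia". It also reports that this redness cleared within 8 hours.

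The analysis sections have a different rule. SAP 7.1.4 says: "The Safety Population will include all randomized subjects who have received at least one dose of study medication". Protocol 9.2 defines the population in the same way. Protocol 9.3.5 (safety), SAP 7.3.2 and SAP 10 summarise observed safety data in it. Under SAP 8.2, major deviations found in a blinded sponsor review before database lock "may result in the removal of a subject's data from the PP Population"; no other population is mentioned. SAP 3.3 declares the SAP consistent with the protocol.

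**The concern.** Two rules govern the same data. Under one, every scheduled safety observation on a treated subject is summarised. Under the other, the sponsor may leave out observations made after a medication question, case by case, with no stated ground and no stated time.

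The second rule is more than a loose end because its trigger can depend on the outcome. A subject bothered by red eyes may reach for a redness-reducing drop. That drop is restricted, its use raises a medication question, and the later visits then become open to exclusion. If redness is commoner on Nyxol than on vehicle, as the earlier studies suggest, such exclusions could fall more often on the Nyxol arm. They would then lower its count of hyperemia and of any other event recorded at those visits. Adverse events are among the primary safety measures, and the safety summaries are descriptive, so no model would correct an under-count.

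**Working it through.** **1. The texts side by side.**

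| Place | What may be left out of the safety summaries | Who decides, and when |
|---|---|---|
| Protocol 6.2 | Visits after a medication question | Sponsor; no criteria, no deadline |
| Protocol 9.2 and 9.3.5 (safety) | Nothing that was observed | Not applicable |
| SAP 7.1.4, 7.3.2 and 10 | Nothing that was observed | Not applicable |
| SAP 7.3.1 | Unscheduled visits, which are still listed | Fixed rule |
| SAP 8.2 | Nothing; only the PP set is affected | Sponsor, blinded, before database lock |

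Protocol 4.9.1 points the same way as the analysis sections. It lists disallowed medication among the reasons for stopping study drug, yet asks that later safety assessments still be completed. No passage withdraws the 6.2 discretion or says which text governs.

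**2. How far the later visits reach.** The first dose is on the evening of Day 1. The scheduled contacts after that are Day 8, Day 15, Day 16 and the Day 22 call, four in all.
- Medication question before the Day 8 visit: 4 of 4 contacts are open to exclusion.
- Between Day 8 and Day 15: 3 of 4.

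**3. Which safety data are exposed.** Doses are taken at 8PM to 10PM and clinic grading starts at 8AM, which is 10 to 12 hours later. With the 15-minute window the shortest gap is 10PM to 7:45AM, or 9.75 hours. Earlier redness cleared within 8 hours. On the plan's own figures, dose-related redness would usually have gone before grading. Events that subjects report at the later visits are therefore more exposed than clinic redness grades.

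**4. Scale, as an illustration only.** The plan's figure reproduces: 36 / (1 - 0.10) = 40 randomised, and 40 / 2 = 20 per arm. Let x of 20 Nyxol subjects have a redness event, and let k of them have their only record in excluded visits. The reported rate is (x - k)/20 if they stay in the denominator, as the Safety Population definition implies. It is (x - k)/(20 - k) if they leave it. The documents give no value for x or k, so the range below is assumed.

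| True rate | k | Denominator kept | Denominator reduced |
|---|---|---|---|
| 4/20 = 20% | 1 | 3/20 = 15% | 3/19 = 15.8% |
| 4/20 = 20% | 2 | 2/20 = 10% | 2/18 = 11.1% |
| 8/20 = 40% | 1 | 7/20 = 35% | 7/19 = 36.8% |
| 8/20 = 40% | 2 | 6/20 = 30% | 6/18 = 33.3% |
| 12/20 = 60% | 1 | 11/20 = 55% | 11/19 = 57.9% |
| 12/20 = 60% | 2 | 10/20 = 50% | 10/18 = 55.6% |

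Each such subject costs 1/20 = 5 points with the denominator kept. For k = 1 the loss is about 2 to 4 points if the subject also leaves the denominator.

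**The case against.** The strongest reply is that the SAP governs the analysis and contains no such exclusion. Run as written, it keeps these visits, and it lists every adverse event, examination and vital sign by subject. The 6.2 sentence covers later visits only: the subject remains in the Safety Population and earlier data count. It names no product, and its link to restricted medication comes from where it stands. Redness drops are one example among several drug classes. The documents give no rate of their use in either arm. Protocol 4.6 masks the sponsor, and safety data are not formally tested.

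All of those facts stand, and they limit the point to a conflict with a possible, unquantified bias. They do not remove it. The SAP does not say that it overrides 6.2, and SAP 3.3 claims agreement with the protocol. Listings do not correct a summary table. Masking limits deliberate selection, but 6.2 does not tie the decision to the masked period, and a trigger related to outcome can bias results even when the decision is masked.

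A reader might infer something stronger: that subjects with the drug's main adverse effect can be removed, and that dropping one could erase a severe-redness signal. The text does not reach subjects, only later visits. The severe-redness step rests on three mild-to-severe shifts in more than 100 subjects, pooled over 0.2% to 1.0% doses. That is under 3%, or fewer than 0.03 x 20 = 0.6 expected cases in 20. Even at 3%, the chance of no severe case among 20 is 0.97^20, about 54%, so more likely than not there would be none to lose. Nothing in the documents links severe redness to use of drops or to an exclusion.

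**Conclusion.** The conflict is real and unreconciled. Protocol 6.2 permits case-by-case exclusion of later safety visits, with no criteria, timing or masking condition. Protocol 9.2, SAP 7.1.4 and SAP 8.2 leave no room for it. This conclusion rests on the text alone and on no assumed rate.

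That exclusions could be related to outcome is a reasonable inference from two stated facts: redness drops are among the restricted products, and hyperemia is the most frequent earlier adverse event. That they would occur more often on Nyxol, and so favour it, is possible but not shown. The size is unknown. The 5-point figure per subject assumes 20 per arm, a subject whose only event falls in excluded visits, and a denominator kept at 20. The sponsor should correct this before unmasking; it does not by itself invalidate the safety analysis.

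**What to change.** Delete the words *safety and* from the sponsor-judgement sentence in Protocol 6.2. Alternatively, state in SAP 10 that all scheduled-visit safety data and all treatment-emergent adverse events of Safety Population subjects are summarised whatever concomitant medication was used, with that medication flagged in the listings. If the SAP route is chosen, say that this text replaces the 6.2 discretion and record the difference in SAP 3.3.

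For efficacy, replace the open judgement with the route already in SAP 8.2: a blinded review finalised before database lock, affecting the PP population only.

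The cost is about one sentence in either document, with no new data and no change to how subjects are managed. The one small drawback is that some redness grades may be taken under a redness-reducing product; the flag would show which.

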7. ASSESSMENT OF EFFICACY

7.1. Specification of the efficacy parameters

The primary efficacy endpoint is the change from Baseline to Day 15 in mean diurnal IOP. Mean diurnal IOP is the mean of the IOP measurements at all three timepoints (8AM, 10AM, 4PM).

IOP is measured with the Goldmann Applanation Tonometer, using a two-person method (one-person physically applies the tonometer, while another reads the result)¹¹.

The eye with the higher IOP at the Qualification Visit at 8AM is designated as the study eye. In the case where both eyes have the same IOP, the study eye will be the RIGHT eye. Baseline evaluations will occur before dosing on Day 1; Treatment-study evaluations will occur on Day 8 ± 1 Day and Day 15 ± 1 Day; follow-up evaluations will occur at 8AM on Day 16.

IOP measurements at the Baseline Visit and both Treatment-study Visits will be performed at 8AM, 10AM and 4PM. All IOP measurements have a window of ± 15 minutes with at least 2 hours between the 8AM and 10AM assessments. IOP will be measured twice in both eyes at each timepoint. The mean value at each timepoint for the study eye will be used in efficacy assessments. If the difference in the two IOP measurements is > 5mmHg, a third measurement will be obtained, and the three values averaged.

7.2. Assessing, recording, and analyzing of efficacy parameters

IOP, visual acuity, and ophthalmological examinations will be measured at the Screening Visit, the Qualification/Baseline Visit, the Treatment-study visits, and Follow-up Visit.

Efficacy Endpoint	Equipment Name	Measurement (Unit)	Procedure
IOP	[REDACTED]	mmHg	[REDACTED]

Distance VA	[REDACTED]	Letters	[REDACTED]
Near VA	[REDACTED]	Jaeger	[REDACTED]
Pupil diameter	[REDACTED]	mm	[REDACTED]

For this study photopic and mesopic light conditions are considered to be “with the lights on or with the lights off”. There are no specific light conditions required other than the same light conditions should be used throughout the study.

7.2.1. Screening

Individuals who are potential subjects will be contacted by the study center to schedule the Screening visit. This visit may occur anytime but at least 28 days and no more than 35 days before dosing.

Once subjects arrive at the study center, a member of the study center staff will interview the individual as to their qualifications for participation in the study, and if the subject wishes to continue, a Screening number is assigned, and the Informed Consent form is signed. Screening includes an explanation of the study, a medical and ophthalmic history, visual acuity exam, heart rate and blood pressure, and a review of concomitant medications. The second step in screening includes procedures such as a urine pregnancy test and a complete ophthalmic examination, including IOP, biomicroscopy, gonioscopy, pachymetry, and visual field (if one has not been done within the last 6 months).

Contact or non-contact pachymetry can be performed providing the same type of pachymeter is used throughout the study for all subjects at an individual site.

Visual field tests of 24-2 or 30-2 are acceptable.

7.2.2. Washout Period

After Screening, study participants will be required to refrain from administration of any glaucoma drugs for at least 28 days and no more than 35 days prior to the Qualification/Baseline Visit. The washout subjects will be brought back in approximately two weeks after the Screening Visit for an IOP safety check. In the judgement of the investigator, if there is any risk to the eye(s) of the subject, or if the mean IOP in either eye is >30 mmHg, then an appropriate rescue or prior medication will be administered, and the subject will be considered a screen failure. Adverse events occurring during the washout period and a review of concomitant medications will also be assessed at this visit.

Unmedicated subjects who meet the inclusion/exclusion criteria after screening do not have a washout period. These subjects may return the following day or up to 35 days later for their Qualification/Baseline Visit.

